We will use the TOST (Two One Sided t-tests) method for equivalence testing. This method requires a defined range of mean differences between two test methods, an estimate of the precision of the measurement of the two systems, and an estimate of the size of the possible difference in the means of the two methods under consideration. The TOST null hypothesis is a joint null hypothesis that the mean measurement differences between the two methods is greater than a critical lower bound and less than a critical upper bound. If the null is rejected then we can conclude that the absolute difference of the means for the two groups falls within the specified range. It was determined that to be considered equivalent with respect to accuracy the mean

measurements of the two methods should be within ± 0.2 degrees of each other. Precision tests for Temp-Traq thermometer using accepted ASTM test methods for various combinations of temperature and humidity provided a range of measurement variation between .0000435 and .019928 with a mean of 0.000254500. If we assume both test methods exhibit the same levels of precision then the variance of the differences between their two means will reduce to two times the values listed previously. This will result in estimates of the standard deviations of the mean differences of .0093, .032, and .063 respectively.

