The two methods for body temperature that will be examined are core temperature measurements with a PA catheter and temperature measurements using the Temp-Traq. Paired temperature measurements for both methods will be taken simultaneously every 2 hours for a 6 hour period. This will provide 4 repeated temperature measures per patient. The simultaneous measurements within a given patient should exhibit a high degree of correlation. If .7 is chosen as the lower bound for the correlation between the paired readings (higher correlations would result in an estimate of fewer patient samples thus the choice of .7 is conservative) and if the average standard deviation of the mean of the differences is used as an estimate of the expected variability, then it would be possible to declare measurement equivalence for a difference of $\pm .19$ with a sample size of 40 patients. This assumes the ASTM measurements of instrument variation are representative of the within patient variance. Given the vagaries of patient-to-patient this may be too optimistic an estimate. Table 1 (attached) is a summary of patient sample sizes for standard deviations equal to the average standard deviation and for 5 and 10 fold increases in this value.

A sample size of 40 patients will provide 80% or greater power for testing for equivalence between methods where the mean difference is .1 or less for up to a ten-fold increase in the estimates of the variability of the differences based on the ASTM precision measures and for a mean difference of .15 for up to a five-fold increase in these same measures. If the sample size is 40 then the power for the test of equivalence, where the difference is .15 and the standard deviation is a ten-fold increase, is 35%. Agreement testing: The Bland-Altman test will be used to test the agreement of the two methods. This test will permit a check for significance of bias between the two measures (the average difference between the two measures) as well as a check for significant trending over the range of the measurements. If the bias is significant then the results of the two differ by an overall offset in their measurements. If the trending (slope of the regression line) is significant then the difference between the two measurements changes as their magnitude changes which means the two methods are not in agreement.

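### Aim 2 has no within-patient precision analysis, and the TOST, bias and slope tests are named without a patient effect although each patient gives four pairs

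*Combined protocol and SAP*

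**What the plan says.** The Design section describes a repeated-measures, within-group study, and Sample/Setting gives 40 patients. Under Procedure, one patch is applied in one axilla, read at baseline (5 minutes after application) and at three further two-hourly points, and removed after the last reading. The Analysis section confirms the count: "This will provide 4 repeated temperature measures per patient".

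Three tests are then named:

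- Equivalence: "We will use the TOST (Two One Sided t-tests) method for equivalence testing". The ±0.2 margin is set for accuracy: "It was determined that to be considered equivalent with respect to accuracy the mean" measurements must lie within it.
- Agreement: "The Bland-Altman test will be used to test the agreement of the two methods". It is described as a test of bias (the average difference),
- and "as well as a check for significant trending over the range of the measurements", by the slope of a regression line.

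None of the three comes with a patient term, a per-patient summary, a clustered error or a unit of analysis. No alpha is given. Aim 2 (Specific Aims) asks about precision across repeated readings. Within-patient variation appears in the Analysis section only as a planning assumption taken from bench tests: "This assumes the ASTM measurements of instrument variation are representative of the within patient variance".

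**The concern.** Two gaps follow.

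First, Aim 2 has no estimator. TOST addresses the mean difference, and Bland-Altman is described only for bias and trend. The overall scatter of the 160 differences would mix variation between patients with variation within them, so it would not answer Aim 2 either.

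Second, four differences from the same patient, under the same patch, may well be correlated. The 0.7 in the Analysis section does not cover this: it is the correlation between the two methods' simultaneous readings, not among one patient's four differences. An analyst could follow the text with 40 patient means, which is valid, or with 160 pairs taken as independent. The second choice would raise the error rate of the TOST and the bias test if the differences are positively correlated within patient. It would raise that of the slope test only if temperature is correlated within patient as well.

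**Working it through.** **Inputs.** From the document: 40 patients, 4 pairs each, margin ±0.2, average SD 0.032 (0.32 at ten-fold), between-method correlation 0.7. Assumed: one-sided 5% per TOST test, and the intraclass correlation (ICC) of a patient's four differences, shown over a range because the document gives none.

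**1. Reproduce the stated power.** SD of a difference at ten-fold = 0.32 × √(2 × (1 − 0.7)) = 0.248. Hand check for a true difference of 0.15: SE = 0.248/√40 = 0.0392; (0.2 − 0.15)/0.0392 − 1.685 = −0.41; Φ(−0.41) ≈ 34%. Integrating over the sample variance gives:

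| Differences | One-sided alpha | True difference | SD | Power | Plan |
|---|---|---|---|---|---|
| 40 | 5% | 0.10 | 0.248 | 80.6% | at least 80% |
| 40 | 5% | 0.15 | 0.124 | 80.6% | at least 80% |
| 40 | 5% | 0.15 | 0.248 | 34.8% | 35% |
| 160 | 5% | 0.15 | 0.248 | 81.5% | 35% |
| 40 | 2.5% | 0.10 | 0.248 | 70.1% | at least 80% |
| 40 | 2.5% | 0.15 | 0.248 | 23.7% | 35% |

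Leaving out the 0.7 correlation (SD 0.32, n = 40, 5%) gives 25.0% at 0.15. Of the variants tried, only one difference per patient at one-sided 5% matches the plan's figures.

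**2. Error rates if 160 pairs were treated as independent.** The true variance of the mean is then 1 + 3 × ICC times the one assumed. TOST size at the margin = Φ(−1.645/√(1 + 3 ICC)); two-sided bias test = 2Φ(−1.96/√(1 + 3 ICC)). For a true difference d beyond the margin, TOST error = Φ((−1.645 − (d − 0.2)/0.0196)/√(1 + 3 ICC)), where 0.0196 = 0.248/√160.

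| ICC | 1 + 3 ICC | TOST at 0.20 | TOST at 0.22 | TOST at 0.25 | Bias test |
|---|---|---|---|---|---|
| 0 | 1.0 | 5.0% | 0.4% | <0.1% | 5.0% |
| 0.3 | 1.9 | 11.6% | 2.7% | 0.1% | 15.5% |
| 0.5 | 2.5 | 14.9% | 4.6% | 0.4% | 21.5% |
| 0.7 | 3.1 | 17.5% | 6.5% | 0.9% | 26.6% |

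Slope test, simulated with 20,000 trials per cell at difference ICC 0.3 to 0.7: about 5% if temperature is uncorrelated within patient, 8.4% to 12.4% at temperature ICC 0.3, and 13.4% to 23.6% at 0.8. With patient means, the TOST and bias tests hold 4.6% to 5.2%; a slope test with a random patient intercept holds 4.2% to 5.7%.

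**3. What Aim 2 could yield.** Within-patient degrees of freedom are 160 − 40 = 120, or 117 with time point as a fixed effect. The 95% limits for the SD are the estimate times √(df/χ²). At 117 df the factors are 0.887 and 1.147, that is −11.3% to +14.7%; at 120 df, −11.2% to +14.5%. This assumes complete data and constant within-patient variance.

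**4. Power with patient means, difference 0.1, one-sided 5%.** If 0.248 is the total SD of a difference, the SD of a patient mean is 0.248 × √(ICC + (1 − ICC)/4) = 0.171, 0.196 and 0.218 at ICC 0.3, 0.5 and 0.7, and power is 98%, 94% and 89%. If 0.248 were the within-patient SD, it is 0.248 × √(ICC/(1 − ICC) + 1/4) = 0.204, 0.277 and 0.398, and power is 92%, 72% and 46%.

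**The case against.** The strongest reply is that the harm in step 2 comes from an analysis the plan does not describe. The sizing counts patients ("A sample size of 40 patients will provide 80% or greater power for testing for equivalence between methods"), the design is labelled repeated measures, and the quoted power, "where the difference is .15 and the standard deviation is a ten-fold increase, is 35" per cent, fits one difference per patient. This stands: a reader might infer that the plan pools 160 pairs as independent, but nothing in the text says so. It leaves the unit to be deduced from a power calculation, and never says how four pairs become one value.

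The error rates are also conditional. They need an assumed ICC, and the TOST inflation is worst exactly at the margin and falls quickly beyond it. Inflated bias and slope tests work against the device, because the plan reads a significant bias as an offset and a significant slope as lack of agreement. Only the TOST error favours equivalence. All of this is accepted.

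A reader might also infer from the second branch of step 4 that 40 patients are too few (80% power would take 28, 49 or 100 patients at ICC 0.3, 0.5 and 0.7). The document gives this little support. The Analysis section raises the five- and ten-fold SDs directly after mentioning patient-to-patient variation, which suggests that the larger SD was meant to absorb it. The sentence on within-patient variance refers to the uninflated bench value.

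Finally, this is a feasibility study, and limits of agreement usually accompany a Bland-Altman analysis. But the plan does not name them, and they would not isolate within-patient precision. Table 1 and the protocol attachment are not in the text available; Table 1 is described as sample sizes only.

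**Conclusion.** The point holds in two parts.

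The Aim 2 gap is the firmer one and depends on no assumed ICC: one of three stated aims has no named within-patient estimate, although the planned data support one with a 95% interval of about −11% to +15%.

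The Aim 1 gap is an omission, not a demonstrated error. The sizing implies the patient as unit and the tests do not carry this through. If pairs were pooled, false equivalence at exactly 0.2 would be 11.6% to 17.5% for ICC 0.3 to 0.7 (one-sided 5% assumed), the bias test would reject in 15.5% to 26.6%, and the slope test in about 5% to 24%. At ICC 0 nothing is inflated.

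The stated power is not wrong given its inputs. With 0.248 as the total SD of a difference, 40 patients are enough for a difference of 0.1. The plan should be amended before analysis; the design need not change.

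**What to change.** - **Unit and model.** Analyse TempTraq minus PA in a linear mixed model with a random patient intercept and time point as a fixed effect, for both TOST and bias. Patient-mean differences with 39 df are an acceptable alternative. State the alpha; one-sided 5% corresponds to a 90% interval.
- **Slope.** Test it in a model with a patient effect.
- **Limits of agreement.** Report them from between-patient plus within-patient variance.
- **Aim 2.** Report the within-patient SD of the differences with its 95% interval. Describe it as single-patch repeatability over time. It includes PA catheter error and real change in the axilla-to-core gap, and excludes patch-to-patch variation because each patient wears one patch. It is therefore not an upper bound on total device imprecision. State the constant-variance assumption and check it, for example with and without the 5-minute reading.
- **Power.** State that the ten-fold SD of 0.248 is the total SD of a difference. If the within-patient SD was meant, restate the power: at a difference of 0.1 it falls below 80% once the ICC exceeds about 0.43.

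The cost is a few lines of SAP text and intervals wider than a pooled 160-pair analysis would give. No new data are needed.

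### The .7 correlation is not a conservative choice: it shrinks a standard deviation that is already on the difference scale, and the stated powers for 40 patients depend on it

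*Combined protocol and SAP*

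**What the plan says.** All of this is in the Analysis section of the combined protocol and SAP.

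- **Test and margin.** "We will use the TOST (Two One Sided t-tests) method for equivalence testing". For accuracy, the mean "measurements of the two methods should be within ± 0.2 degrees of each other". No alpha is stated.
- **Instrument variance.** ASTM bench testing gave "a range of measurement variation between .0000435 and .019928 with a mean of 0.000254500".
- **Difference scale.** With both methods assumed equally precise, "the variance of the differences between their two means will reduce to two times the values listed previously", which yields "estimates of the standard deviations of the mean differences of .0093, .032, and .063 respectively". The later calculations start from the average, .032, and from five-fold and ten-fold multiples of it.
- **Correlation.** The sample-size paragraph then takes .7 as a lower bound for the correlation between simultaneous readings and defends it: "higher correlations would result in an estimate of fewer patient samples thus the choice of .7 is conservative".
- **Power.** "A sample size of 40 patients will provide 80% or greater power for testing for equivalence between methods" when the true difference is .1 with ten-fold variability or .15 with five-fold variability. At .15 with ten-fold variability the power is given as 35%. At the base SD, 40 patients are said to suffice for a difference of ±.19. The closing paragraph calls the power at .1 with ten-fold variability acceptable.

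Table 1, which holds the sample sizes, is an attachment not included in the document.

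**The concern.** Write each reading as the patient's true temperature plus instrument error. Two simultaneous readings correlate because they share the true temperature, and subtracting one from the other removes that shared part. The difference contains only the two errors.

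The ASTM variances are bench figures for instrument error and contain no patient temperature variation. Doubling them already gives the variance of a difference with independent errors. Nothing is left for a correlation between readings to remove, unless the two devices' errors are themselves correlated.

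A higher correlation between readings can simply mean that temperatures vary more, as they would in a study that aims to cover hypothermia to hyperthermia. Finding a correlation above .7 would then say nothing about whether the SD of differences is as small as planned. The power statements are the main justification for 40 patients, so the basis for that number would not be the one given.

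**Working it through.** **Inputs.** From the Analysis section: N = 40; margin m = 0.2; mean ASTM variance .0002545; labelled SD of differences .032 with multipliers 1, 5 and 10; correlation .7; true differences d = .10, .15 and .19. Assumed: one-sided alpha .05 for each test. The calculation uses one difference per patient.

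**Method.** Exact paired TOST power with 39 degrees of freedom. As a hand check, power is approximately Φ[(m - d)/(SD/√40) - 1.645].

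**Step 1: reproduce the plan's figures.** Use SD = .032 x multiplier x sqrt(2 x (1 - .7)), that is, .032 x multiplier x .775.

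- .10, ten-fold: SD = .32 x .775 = .248 and SE = .248/√40 = .0392. By hand, .10/.0392 - 1.645 = .91, or 81.8%; exact 80.6%.
- .15, five-fold and .19, one-fold: (m - d)/SD before the factor is .05/.16 and .01/.032. Both equal .3125, as does .10/.32, so the exact power is again 80.6%.
- .15, ten-fold: by hand 35.6%; exact 34.8%.
- N = 40 is the smallest sample that reaches 80% exactly at .10, ten-fold.

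These match every stated figure. Other readings of the inputs do not:

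| SD of difference at ten-fold | Alpha | .10, ten-fold | .15, ten-fold |
|---|---|---|---|
| .32 x √.6 = .248 | .05 | 80.6% | 34.8% |
| .32 x √.6 = .248 | .025 | 70.1% | 23.7% |
| .32 x √.3 = .175 | .05 | 97.1% | 55.1% |
| .32, no correlation | .05 | 61.7% | 25.0% |
| .32, 160 readings taken as independent | .05 | 98.9% | 62.7% |
| .226 x √.6 = .175 | .05 | 97.2% | 55.3% |

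**Step 2: does the factor belong?** Let true temperature have variance T and each device independent error variance E. The correlation between readings is ρ = T/(T + E). The formula 2 x (total variance) x (1 - ρ) becomes 2(T + E) x E/(T + E) = 2E. So (1 - ρ) is correct only when multiplied by the total variance T + E. Multiplied by an error variance, it removes T a second time. A simulation with error SD .32/√2 per device gave an SD of differences of .320 at correlations of .3, .7 and .95.

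**Step 3: is .032 the right starting SD?** The section's own rule gives sqrt(2 x .0000435) = .0093, as printed. For the mean it gives sqrt(2 x .0002545) = .0226, not .032; the printed value matches sqrt(4 x .0002545) = .0319, as if doubled twice. The SD effectively used, .032 x .775 = .0248, is larger than .0226. The upper value has a similar mismatch: .063 fits a variance of .0019928, whereas the printed .019928 gives .20.

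**Step 4: power without the .7 (N = 40, alpha .05).**

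| Base SD of differences | .10/ten-fold, .15/five-fold, .19/one-fold | .15/ten-fold | N for 80% at .10/ten-fold |
|---|---|---|---|
| .032 (as labelled) | 61.7% | 25.0% | 65 |
| .0226 (from .0002545) | 86.6% | 39.5% | 33 |
| Plan: .032 with .7 | 80.6% | 34.8% | 40 |

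**The case against.** **The stated powers are not miscalculated.** A reader might infer that 80% and 35% are arithmetic errors. They are not: they follow from the plan's inputs once .7 is applied. The dispute is over an input.

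**The direction is not settled.** A reader might also infer that the .7 has inflated power and that 40 patients are too few. That holds only if .032 is correct. On the printed mean variance, the unexplained enlargement to .032 more than offsets the .7 shrinkage, and 80% or more stands. Nor does the document support treating .032 as each device's SD (about 39% and 17% with no correlation), since it labels that figure an SD of differences.

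**There is another safety margin.** The plan concedes that bench variation may be too optimistic for patients and covers five-fold and ten-fold increases in the SD. That outweighs a factor of 1/.775 = 1.29. This stands, so the correlation is not the plan's only protection. But the inflated scenarios carry the same .775.

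**Four readings per patient.** If the four differences were averaged and their errors were independent over time, the SD would halve, and .32 would give 98.7% and 61.7%. The plan does not say that it averages, its stated figures do not reflect averaging, and a persistent patient-level offset would reduce the gain. What stands is that the figures here are for a single difference per patient.

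**Unseen material.** Alpha is assumed, and Table 1 might define the SD. But .05 reproduces the stated figures and .025 does not.

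**Conclusion.** The concern holds in a limited form. The .7 is applied to an SD that the plan presents as already being for differences, and the reason given for it does not bear on instrument error. That a higher correlation lowers N is true inside the formula, but it does not make .7 conservative here.

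The size depends on a second inconsistency that only the sponsor can resolve. Without the .7, power in the three 80% scenarios is 61.7% or 86.6%, and in the 35% scenario 25.0% or 39.5%, according to whether .032 or .0002545 is right. The documents therefore do not establish that the study is underpowered; they establish that the stated powers lack a sound derivation.

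This rests on one-sided alpha .05, one difference per patient, device errors independent of each other, and both devices responding equally to a change in true temperature.

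**What to change.** In the Analysis section:

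1. Delete the .7 and the claim that it is conservative, or justify .7 explicitly as a correlation between the two devices' errors.
2. State which of .032 or .0226 is the SD of paired differences, and correct the variance or the SD accordingly.
3. State alpha for each one-sided test.
4. Rerun Table 1 on that SD with no further correlation factor. Restate the 80%, 35% and ±.19 figures and the closing paragraph's description of the power as acceptable.
5. Keep N = 40 with the restated power beside it. If .032 is right, say plainly that power at a difference of .10 with ten-fold variability is about 62%.

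The cost is rewording and one rerun of Table 1. No additional patients are needed, though the stated power may become less favourable.

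### The ASTM variances, the SDs of the differences and the 80%/35% power that justify N = 40 do not agree, and the planning SD cannot be identified from the text

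*Combined protocol and SAP*

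**What the plan says.** All of this is in the Analysis section, which plans a TOST with a margin of ±0.2 degrees.

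- **Inputs.** ASTM testing gave "a range of measurement variation between .0000435 and .019928 with a mean of 0.000254500". With equal precision in both methods, "the variance of the differences between their two means will reduce to two times the values listed previously", which is said to give "estimates of the standard deviations of the mean differences of .0093, .032, and .063 respectively".
- **Planning value.** The sample-size paragraph begins "If .7 is chosen as the lower bound for the correlation between the paired readings" and goes on "if the average standard deviation of the mean of the differences is used as an estimate of the expected variability". On that basis, 40 patients suffice to declare equivalence at a difference of ±.19.
- **Power.** The main claim reads "A sample size of 40 patients will provide 80% or greater power for testing for equivalence between methods where the mean difference is .1"; it extends to smaller differences and to variability as high as ten times the base. The same is claimed at .15 for up to five times. At .15 with ten times the base, power is put at 35%.
- **Table 1.** "Table 1 (attached) is a summary of patient sample sizes for standard deviations equal to the average standard deviation"; it also covers five and ten times that value.
- **Closing paragraph.** Power at .1 with a ten-fold increase is called acceptable, but here the increase is applied to the minimum test variability.

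The text available gives no alpha. On repeated readings it says "This will provide 4 repeated temperature measures per patient", but not how they enter the TOST.

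**The concern.** These numbers are the stated reason for 40 patients. The variances should lead to the SDs by the rule the plan gives, and the SDs should lead to the stated power. Neither step works as printed. A reader cannot tell which SD the 80% refers to, whether it belongs to one method or to the paired difference, or whether the base is an average or a minimum. The plan itself warns that bench-test variation may be too optimistic for patients. Its answer to that warning is the five- and ten-fold cases, and these are multiples of the base value in question.

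**Working it through.** **Step 1: variances to SDs, by the plan's doubling rule, SD = √(2 × variance).**

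| ASTM value | √(2 × value) | Printed SD |
|---|---|---|
| .0000435 (minimum) | .0093 | .0093 |
| .0002545 (mean) | .0226 | .032 |
| .019928 (maximum) | .200 | .063 |

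The variances are listed as minimum, maximum, mean, while the SDs rise in size. Pairing them in printed order does not help, because neither .0226 nor .200 is printed at all. Two observations, neither of which settles the source: .032 is 2 × √.0002545 = 2 × .0160, that is, four times the variance rather than twice; and .063 would follow from .0019928, since √(2 × .0019928) = .0631.

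**Step 2: reproduce the stated power.** Inputs from the plan: n = 40, margin .2, correlation .7, average SD .032. Assumed: alpha .05 per side and one difference per patient. The method is exact paired TOST power with 39 degrees of freedom, integrating over the sample variance.

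If .032 is a per-method SD, the SD of the difference is .032 × √(2(1 − .7)) = .0248, or .248 at ten-fold. Power is 80.6% at .1 ten-fold and 34.8% at .15 ten-fold. With 39 patients the first figure falls to 79.7%, so 40 is the smallest n reaching 80%. This matches the plan.

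**Step 3: use .032 as labelled, as an SD of differences.** The three claims tied to N = 40 share one ratio of distance-to-margin over SD:

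- .19 at base: .01/.032 = .3125
- .15 at five-fold: .05/.16 = .3125
- .1 at ten-fold: .10/.32 = .3125

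They therefore have the same power. Hand check: .3125 × √40 = 1.98, against a critical t of 1.685, gives Φ(.29) ≈ 61%; the exact figure is 61.7%. At .15 ten-fold the exact figure is 25.0%.

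**Step 4: is the match in Step 2 unique?** The average SD can also be read literally as the mean of the three printed SDs: (.0093 + .032 + .063)/3 = .0348. Multiplied by √(1 − .7²) = .714, this is again .0248. Power is 80.5% and 34.7%, and 40 is again the smallest n.

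**Step 5: spread over readings (n = 40, ten-fold SD).**

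| Base SD of the difference | Power at .1 | Power at .15 |
|---|---|---|
| .0348, mean of three SDs, used directly | 55.7% | 22.6% |
| .032 as labelled | 61.7% | 25.0% |
| .0248, from .032 per method with .7 | 80.6% | 34.8% |
| .0226, the doubling rule | 86.6% | 39.5% |
| .0093, the minimum | near 100% | 95.5% |

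The last row is what the closing paragraph describes if its reference to the minimum is taken literally. The third row reproduces what the power paragraph reports.

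**The case against.** The best defence is that the power arithmetic may be sound and only the labels wrong. If .032 is a per-method SD, then 80%, 35% and N = 40 all come out. That is the most natural match, and it may be what was run. It does not rescue the text: the plan calls .032 an SD of differences, and as a per-method SD it still disagrees with the printed mean variance, because √.0002545 = .0160.

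A reader might go further and infer that the plan provably applied the variance-of-a-difference step twice. The documents do not support that. Alpha is assumed, Table 1 was not available, and Step 4 shows a second route to the same figures, although √(1 − .7²) is a less usual factor for a paired TOST. Averaging the four readings would also give the pair from an SD of .32 if the within-patient correlation of the differences were .467, a value the plan does not state.

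It is also fair to say that 80% or greater is an inequality, which the doubling rule's .0226 satisfies at 87%. But that SD gives 39%, not 35%, at .15. Finally, this is a feasibility study that admits its variability estimate may be too small. That limits the consequence, but the admission is answered only by multiples of the same unsettled base.

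**Conclusion.** The figures are wrong as written. The two SD mismatches (.0226 against .032, and .200 against .063) need no assumption beyond the plan's own rule. The power mismatch (62% and 25% as labelled, against 80% and 35% as stated) rests on alpha .05 per side and one analysed difference per patient. The planning SD cannot be identified from the text, and the power and closing paragraphs name different bases, average and minimum.

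A reader might infer that the trial is underpowered. That does not follow: among the readings tabulated, power at .1 ten-fold runs from 56% to near 100%, so the direction of the error is open. This is a correction to the justification of the sample size, not a case for changing it.

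**What to change.** Keep N at 40 and make these changes in the Analysis section:

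1. Check .0002545 with .032, and .019928 with .063, against the ASTM source and correct whichever is wrong.
2. State which SD is the planning value, and whether it is per method or of the paired difference. If it is already an SD of paired differences, do not apply the .7 correlation again.
3. Reconcile the average in the power paragraph with the minimum in the closing paragraph before keeping the statement that power is acceptable.
4. State alpha and how the four readings form the analysed per-patient difference, then restate the power there and in Table 1 by the SD of that difference.

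Usable text: *With 40 patients, margin .2 and alpha .05 per side, power is about 80% at a true difference of .1 if the SD of the analysed difference is about .25, at .15 if about .125, and at .19 if about .025; smaller SDs give more.*

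If .032 is kept as the SD of the analysed difference, print 62% and 25%. If it proves to be per method, 80% and 35% can stay, and the label and the printed mean variance are corrected.

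The cost is a source check and rewording, with no added patients or procedures. The one downside is that the stated power may become less favourable.
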